#### 7.6.8 SUBGROUP ANALYSES

After unblinding, it was decided to perform various subgroup analyses of OS. The subgroup analyses will be performed by the following assessments at Screening or Baseline:

CP Score at Screening (7, 8, 7+8, or 9), Sex, ECOG PS at Screening (0 or 1+2).

AFP (≤400 ng/mL or >400 ng/mL) at Baseline,

Prior Locoregional therapy (HCC Prior Therapies of Radiation or

Chemoembolization =Yes, Otherwise =No),

EHS (Yes or No), PVT (Yes or No), and Either EHS or PVT (Yes or No),

History of HBV (Known history of HBV=Yes or No),

History of HCV (Known history of HCV=Yes or No),

Diagnostic Procedure (Cytology/histology or AASLD), and

Country (based on the first digit of the site number, given as Bulgaria=1, Serbia=2, Israel=3, Romania=5, or United States=7).

The subgroup analyses will be performed as univariate analyses within each level of the corresponding subgrouping variable. For each subgrouping variable, the between-treatment comparisons will be performed using the logrank test (Section 7.6.1). Each analysis will include the hazard ratio with the corresponding 95% confidence interval from proportional hazards model with no additional covariates and the p-value (Chi-Square), as described in Section 9. The subgroup analyses do not include a plot of each KM curve, except for the analyses by CP Score at Screening (CP=7, CP=8, or CP=7 or 8), and do not include the value of the KM curve at the median duration of therapy, provided in the analyses for the ITT Population.

History of viral hepatitis is recorded as "Yes, Hepatitis B"; "Yes, Hepatitis C"; "No"; or "Not known", with the date of diagnosis recorded for the first two responses, both of which are possible. If both of these responses are recorded, then the response for both History of HBV and History of HCV will be considered "Yes". Subjects with responses of "Not known" will be excluded from the subgroup analyses using history of viral hepatitis.

Subgroup analyses for other time-to-event variables or tumor response variables may be presented as further exploratory analyses after review.

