After unblinding, it was decided to present incidence of EHS and PVT at Baseline (Section 7.4.2), which are not given in the protocol.

Any changes not presented in this or any subsequent version of the SAP will be described in the clinical study report.

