Programming Notes: Do not skip numbers for liver lesions for 1 through 5. There should be no subjects with 0 liver lesions or more than 5 liver lesions; if these are observed, include them as above, but otherwise only 1 through 5. Include only non-zero counts. For non-liver lesions, exclude rows with no entries. If any subjects have only liver lesions, include "None" row as non-liver site code. The values will be the counts of lesions at "Screening" from Listing 16.2.6.1.1.

11 = Pancreas, 12 = Pelvis, 13 = Pleura, 14 = Rectum, 15 = Retroperitoneal Cavity, 16 = Retroperitoneum, 17 = Small Intestine, 18 = Uterus, 99 = Other

 Number of non-liver lesions may not sum to Total due to subjects with more than one non-liver site.

Table 14.1.4.3

Extrahepatic Spread (EHS) and Portal Vein Thrombosis (PVT)
Safety Population

		CF102	Placebo	Total
Parameter, n (%)		(N=xx)	(N=xx)	(N=xx)
Extrahepatic Spread (EHS)	Yes	xx (xx.x)	xx (xx.x)	XX (XX.X)
	No	xx (xx.x)	xx (xx.x)	xx (xx.x)
	Total	XX	xx	xx
Portal Vein Thrombosis (PVT)	Yes	xx (xx.x)	xx (xx.x)	xx (xx.x)
` ,	No	xx (xx.x)	xx (xx.x)	xx (xx.x)
	Total	xx	xx	хх
Either EHS or PVT	Yes	xx (xx.x)	xx (xx.x)	xx (xx.x)
	No	xx (xx.x)	xx (xx.x)	xx (xx.x)
	Total	xx	xx	хх
Both EHS and PVT	Yes	xx (xx.x)	xx (xx.x)	xx (xx.x)
	No	xx (xx.x)	xx (xx.x)	xx (xx.x)
	Total	xx	xx	хх

Percentages are calculated using the number of subjects for each treatment (or Total) as the denominator.

Source: Listing 16.2.3.3.2

Programming Note: "Either EHS or PVT"= "Yes" if EHS= "Yes" or PVT= "Yes" and otherwise "Either EHS or PVT"= "No". "Both EHS and PVT"= "Yes" if EHS= "Yes" and PVT"= "Yes" and otherwise "Both EHS and PVT"= "No".

Table 14.1.5

Medical History (Excluding Past HCC, Cirrhosis, and Viral Hepatitis-Related History)
Safety Population

	CF102	Placebo	Total
Body System, n (%)	(N=xx)	(N=xx)	(N=xx)
None	xx (xx.x)	xx (xx.x)	xx (xx.x)
Allergy/Immunological	xx (xx.x)	xx (xx.x)	xx (xx.x)
Cardiovascular	xx (xx.x)	xx (xx.x)	xx (xx.x)
Dermatological	xx (xx.x)	xx (xx.x)	xx (xx.x)
ENT	xx (xx.x)	xx (xx.x)	xx (xx.x)
Gastrointestinal/ Hepatobiliary	xx (xx.x)	xx (xx.x)	xx (xx.x)
Hematological/ Lymphatic	xx (xx.x)	xx (xx.x)	xx (xx.x)
Metabolic/Endocrine	xx (xx.x)	xx (xx.x)	xx (xx.x)
Musculoskeletal	xx (xx.x)	xx (xx.x)	xx (xx.x)
Neoplastic	xx (xx.x)	xx (xx.x)	xx (xx.x)
Neurological/ Psychiatric	xx (xx.x)	xx (xx.x)	xx (xx.x)
Pulmonary	xx (xx.x)	xx (xx.x)	xx (xx.x)
Renal/Urological	xx (xx.x)	xx (xx.x)	xx (xx.x)

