# Listing 16.2.3.3.1

**HCC History** 

Site/ Subject	Treatment	Date of Screening Visit	Known History of Viral Hepatitis?	Date of Diagnosis of Hepatitis B	Date of Diagnosis of Hepatitis C	Hepatitis B Virus Serology	Date of Last Hepatitis B Testing	Hepatitis C Virus Serology	Date of Last Hepatitis C Testing	Complications (1)
xxx/xxxx	XXXXX	DD/MM/YY	Yes	DD/MM/YY	DD/MM/YY	XXXXXXXXXX	DD/MM/YY	XXXXXXXXXXX	DD/MM/YY	XXXXX
xxx/xxxx	XXXXX	DD/MM/YY	No			XXXXXXXXXX	DD/MM/YY	XXXXXXXXXX	DD/MM/YY	XXXXX
xxx/xxxx	XXXXX	DD/MM/YY	Yes	DD/MM/YY	DD/MM/YY	XXXXXXXXXX		XXXXXXXXXX	DD/MM/YY	XXXXX
xxx/xxxx	XXXXX	DD/MM/YY	Yes	DD/MM/YY		XXXXXXXXXX	DD/MM/YY	XXXXXXXXXX	DD/MM/YY	XXXXX
										XXXXX
xxx/xxxx	XXXXX	DD/MM/YY	Yes	DD/MM/YY	DD/MM/YY	XXXXXXXXXX	DD/MM/YY	XXXXXXXXXX	DD/MM/YY	None
xxx/xxxx	XXXXX	DD/MM/YY	Yes		DD/MM/YY	XXXXXXXXXX	DD/MM/YY	xxxxxxxxx	DD/MM/YY	XXXXX

 Known complication(s) of cirrhosis and/or portal hypertension

Programming Notes: If date of last testing is missing, then the field should be blank. "Serology" should not be blank. If none of the specified responses, including Other, are selected for Complications, then the response should be reported as "None". If "Other, specify" is reported for complication, then report the specified details as the complication. If more than 1 complication is reported, then multiple lines per subject should be used. Date of Screening Visit must match that given in Listing 16.2.2.1.

Listing 16.2.3.3.2

Extrahepatic Spread (EHS) and Portal Vein Thrombosis (PVT)

Site/ Subject	Treatment	EHS	PVT	Either EHS or PVT	Both EHS and PVT
xxx/xxxx	XXXXX	XXX	XXX	XXX	XX
xxx/xxxx	XXXXX	XXX	XXX	XXX	XX

EHS = Extrahepatic Spread, PVT = Portal Vein Thrombosis

Programming Notes: Record each response as "Yes", "No", or "Unknown". Include only subjects with one of these responses recorded.

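### The shell's rule for combining EHS and PVT turns an undetermined status into No, and the Either composite then defines an OS subgroup with no exclusion of undetermined subjects

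*SAP*

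**What the plan says.** EHS and PVT are not in the protocol. SAP Section 9 states: "After unblinding, it was decided to present incidence of EHS and PVT at Baseline (Section 7.4.2), which are not given in the protocol". SAP 7.4.2 calls for a table of their incidence at Baseline, and SAP 7.6.8 adds them as OS subgroups: "EHS (Yes or No), PVT (Yes or No), and Either EHS or PVT (Yes or No").

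The mock tables and listings (Version 7.0) implement this in three places:

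- **Listing 16.2.3.3.2**, the source for both tables, has columns for EHS, PVT, Either and Both. Its note reads: "Record each response as 'Yes', 'No', or 'Unknown'. Include only subjects with one of these responses recorded".
- **Table 14.1.4.3** has only Yes, No and Total rows for each of the four variables. Its note defines the composites: "Either EHS or PVT'= 'Yes' if EHS= 'Yes' or PVT= 'Yes' and otherwise 'Either EHS or PVT'= 'No". For Both, the note requires two Yes responses, "and otherwise 'Both EHS and PVT'= 'No". The footnote on percentages is "Percentages are calculated using the number of subjects for each treatment (or Total) as the denominator".
- **Table 14.2.7.6** gives logrank p-values, hazard ratios and confidence intervals for OS within the Yes and No levels of EHS, PVT and Either. It has no Unknown level and no exclusion rule.

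For a comparable variable, SAP 7.6.8 takes the other course: "Subjects with responses of 'Not known' will be excluded from the subgroup analyses using history of viral hepatitis". The matching baseline table, Table 14.1.4.1, prints a separate row for unknown hepatitis history.

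**The concern.** The source listing recognises three states, and the derivation built on it recognises two. A subject with no EHS and an unknown PVT status has not been shown to be free of both, yet the note classes that subject as No. Any such subjects would make the baseline frequency of Either or Both look lower than the data can support. The Either = No stratum of the OS subgroup would also be labelled as free of both conditions while containing subjects for whom that was never established.

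Unknown responses are plausible, particularly for PVT. The schedule of events (Table 1–1), the disease history in Protocol 9.2.2 and the disease-history list in SAP 7.4.2 do not name it. The CRF options for complications of cirrhosis or portal hypertension, as the SAP describes them, are ascites, bleeding esophageal varices, and a free-text Other. No scheduled assessment is therefore specified to record PVT.

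The subgroups were chosen after unblinding, so the derivation rule should leave no avoidable ambiguity.

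**Working it through.** The plan states no figure that depends on this rule, so there is nothing to reproduce. The check is to run every possible pair of responses through the note and compare the result with what the pair actually establishes.

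| EHS | PVT | Either, by the note | Either, as established | Both, by the note | Both, as established |
|---|---|---|---|---|---|
| Yes | Yes | Yes | Yes | Yes | Yes |
| Yes | No | Yes | Yes | No | No |
| Yes | Unknown | Yes | Yes | No | **Unknown** |
| No | Yes | Yes | Yes | No | No |
| No | No | No | No | No | No |
| No | Unknown | No | **Unknown** | No | No |
| Unknown | Yes | Yes | Yes | No | **Unknown** |
| Unknown | No | No | **Unknown** | No | No |
| Unknown | Unknown | No | **Unknown** | No | **Unknown** |

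- **Either.** The note sends four combinations to No, and only No/No is an established No. Of the five combinations with at least one Unknown, two are correctly Yes and three are undetermined but coded No.
- **Both.** The note sends eight combinations to No, of which three are undetermined. Of the five with at least one Unknown, two are correctly No.
- **EHS and PVT singly.** No text recodes Unknown. The Yes and No rows simply have no place for it. A subject with EHS = No and PVT = Unknown would therefore fit neither PVT level of Table 14.2.7.6 but would be counted in Either = No in the same table.

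**Illustration of size.** None of these inputs except the 78 planned subjects comes from the documents. Assume EHS in 30%, always known; PVT in a proportion p = 35%, independent of EHS; and PVT Unknown in a proportion u, unrelated to true status.

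- Subjects with EHS = No: 78 × 0.70 = 54.6.
- Size of Either = No by the note: 54.6 × [u + (1 − u)(1 − p)].
- Undetermined share of that group: u / [u + (1 − u)(1 − p)]. The number of subjects and the EHS frequency cancel.

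| u | Undetermined subjects | Size of Either = No | Undetermined share |
|---|---|---|---|
| 0% | 0 | 54.6 × 0.65 = 35.5 | 0% |
| 5% | 2.7 | 54.6 × 0.6675 = 36.4 | 7.5% |
| 20% | 10.9 | 54.6 × 0.72 = 39.3 | 28% |
| 30% | 16.4 | 54.6 × 0.755 = 41.2 | 40% |

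At u = 20%, about 10.9 × 0.35 = 3.8 of the 39.3 subjects (10%) would in truth have PVT. Table 14.1.4.3 would then show Either = Yes in 78 − 39.3 = 38.7 subjects (50%), against a true 78 − 35.5 = 42.5 (54%).

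**The case against.** The strongest reply is that there may be no Unknown responses at all. Version 7.0 was prepared after unblinding, and some shell notes already reflect observed data: Table 14.2.7.1 tells the programmer to enter zero placebo subjects at Child-Pugh score 9, and the target-lesion listings report that no case with all target lesions gone occurred. Where the authors expected unknowns, for hepatitis history, they provided a row and an exclusion. Yes/No/Total rows are compatible with complete EHS and PVT data. This stands: the documents cannot settle the count, so the effect has to be stated conditionally.

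Second, the rule is attached to Table 14.1.4.3, whereas Table 14.2.7.6 cites Listing 16.2.3.3.2 as its source. The listing has its own composite columns, and its instruction "Record each response as 'Yes', 'No', or 'Unknown" could be read as allowing an Unknown composite. That is fair, but it leaves two conflicting instructions. The table note is the only definition of the composites, and the subgroup text offers only Yes and No.

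Third, PVT is not necessarily unrecorded. CT or MRI is scheduled at the Pre-Study Visit, disease staging is collected, and the complications field has a free-text option. The CRF itself is not among the documents. Lesion sites are recorded, so EHS has at least a partial source and the gap is chiefly PVT.

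Fourth, the outputs are minor and the SAP discloses that they were added after unblinding. This stands and limits the weight of the point.

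A reader might also infer more than the text allows:

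- **That every Unknown becomes No.** It does not. The note covers only the composites, and an Unknown paired with a Yes is correctly Either = Yes.
- **That the tables do contain misclassified subjects.** No count is given. Subjects with nothing recorded are left out of the listing, so the rule need not reach them.
- **That any imbalance in unknowns biases the subgroup hazard ratio.** The stratum still compares randomised arms. Unknown status unrelated to treatment mainly changes whom the stratum represents.
- **That PVT status was determined after unblinding.** Section 9 dates the decision to present it. It does not date the reading or the recording.

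**Conclusion.** The point holds in a limited form. As written, the note classifies an undetermined EHS/PVT status as No in three combinations for Either and three for Both. This conflicts with the Unknown category in its own source listing and with the SAP's handling of hepatitis history. The Either composite carries the problem into an OS subgroup with no exclusion of undetermined subjects.

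The number of subjects affected is not given and may be zero. The illustrative 0–40% undetermined share of Either = No rests on an assumed 35% PVT frequency, 0–30% PVT Unknown, fully known EHS, and independence of the two conditions. It shows scale and is not an estimate for this trial. Only a descriptive baseline table and an exploratory subgroup are affected. The primary logrank test of OS uses neither variable, and no sample size or significance level depends on them.

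**What to change.** - **Either:** Yes if at least one component is Yes; No only if both are No; otherwise Unknown.
- **Both:** Yes if both are Yes; No if at least one is No; otherwise Unknown.
- **Table 14.1.4.3:** add an Unknown row to each of the four variables.
- **Table 14.2.7.6:** exclude Unknown from each of the EHS, PVT and Either analyses, as SAP 7.6.8 already does for hepatitis history.
- **Clinical study report:** state the source of EHS and PVT status and when each was recorded relative to unblinding.

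The cost is a few lines of shell text and programming, with possibly slightly smaller subgroup counts. If there are no Unknown responses, the results do not change.

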9.2.12 Response Assessment

Response assessments will be performed and documented throughout the trial using RECIST v1.1 ([Appendix A](#)).

The same method/technique for assessing response, either CT scan or MRI, should be used for any individual subject throughout the trial. If progressive disease (PD) is documented at any time, the patient will not be discontinued from the trial. Further imaging or target lesion measurements will not be required and all other trial visits and procedures will continue. Diagnostic studies documenting disease response must be available for review by the Sponsor, if requested.

In the event of an objective response, the duration of the response will be determined from the day the initial response is observed (using the Pre-Study Visit images for comparison) to the day that progression is observed. Duration of stable disease will also be assessed (see [Appendix A](#)).

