#### 6.1 EFFICACY ASSESSMENTS

Tumor response will be assessed at the Pre-Study Visit, Day 1 of odd-numbered cycles, and at the follow-up visit using Response Evaluation Criteria In Solid Tumors (RECIST v1.1) from Eisenhauer et al. (2009), presented in Appendix A of the protocol, and further described below in Appendix B. In general, target lesions will be assessed as Complete Response (CR), Partial Response (PR), Stable Disease (SD), or Progressive Disease (PD) and non-target lesions will be assessed as Complete Response (CR), Incomplete Response/Stable Disease (SD), or Progressive Disease (PD). Tumor responses from target lesions and from non-target lesions will be used to determine Overall Response as described in Appendix B. If the Overall Response is CR or PR, tumor assessments are to be repeated within 4 weeks. Overall Response will be tabulated by cycle and treatment; the responses for target lesions and non-target lesions will be included in listings, but will not be tabulated. If Overall Response of PD is observed at any time, the patient will not automatically be discontinued. Further imaging or target lesion measurements will not be required and all other trial visits and procedures will continue.

If assessments are made after the Overall Response of PD is recorded, then the Overall Response at all subsequent cycles will be PD and will be included at every cycle for which the Overall Response is recorded through Cycle 11 (see Section 7.2).

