#### 7.6.4 TUMOR RESPONSE

The Objective Response Rate (ORR) is the percentage of subjects who achieved either CR or PR. ORR will be summarized using counts and percentages for the ITT Population by treatment and cycle. The between-treatment comparison will be performed using the normal approximation to the binomial distribution (NAB) with unequal variances, as follows.

For each cycle, let  $p_{CF}$  and  $p_0$  denote the proportions of subjects who experienced CR or PR based on  $n_{CF}$  and  $n_0$  subjects for CF102 and Placebo, respectively, and let

 $Z=(p_{CF}-p_0)/(p_{CF}(1-p_{CF})/n_{CF}+p_0(1-p_0)/n_0)^{1/2}$ .

Then the corresponding p-value is p=2\*(1-PROBNORM(ABS(Z))).

The Disease Control Rate (DCR) is the percentage of subjects who achieved either CR, PR, or SD. DCR will be summarized using counts and percentages for the ITT Population by treatment and cycle. The between-treatment comparison will be performed using the (NAB), similar to that for ORR.

For each subject, the Best Overall Response during the duration of the study will be determined and will be summarized using counts and percentages for the ITT Population by treatment. The between-treatment comparison will be performed using the NAB, for both the percentage of subjects who achieved either CR or PR (similar to ORR) and the percentage of subjects who achieved either CR, PR, or SD (similar to DCR).

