#### Table Format Specification

Maximum and minimum values will be reported with the same number of decimal places as collected. Means and medians will be reported to one additional decimal place. Standard deviations and standard errors will be reported to two decimal places more than the collected data. Percents will be reported with one decimal place. P-values will be rounded to three decimal places (e.g., "0.xxx"). If a p-value <0.001, then the p-value will be reported as "<0.001".

If the frequency is 0 or 1 for a category for calculation of a standard deviation or standard error, then enter '(NE)' for calculation of the standard deviation or standard error and add a footnote (penultimate preceding Source) of 'NE= Not Estimable'.

If the frequency for "Total" <2 for a categorical variable for either treatment group, or frequency is "Total" for any category, i.e. a percent of 100 for that category, for both treatment groups, then enter 'NA' for the p-value with a footnote (penultimate preceding "Source") of 'NA = Not Applicable'.

Data in the tables are formatted as follows:

- Text fields in the body of the tables and listings will be left-justified.
- All numeric values between -1 and 1 are outputted with zero to the left of the decimal point (e.g. 0.12, 0.3).
- Unless otherwise specified, percentage values are output with one digit to the right of the decimal point (e.g., 12.3, 4.5). Percentages that are > 0.0 and < 0.1 (not 0.0) are reported as "< 0.1".

- When no data are available for a table, an empty page with the title will be produced with suitable text. Example: THERE WERE NO SERIOUS ADVERSE EVENTS.

For many variables assessed at Pre-Study Visit, Baseline=Cycle 1 Day 1 (or Pre-Study if <= 3 days prior to Cycle 1 Day 1) or if value at Cycle 1 Day 1 is missing. These are variables are identified with a footnote indicating this.

Dates will be presented as recorded. All listings will include the Safety Population and will be sorted by site, subject, and cycle (if appropriate). Treatments are to be formatted as CF102 and Placebo in listings.

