Percentages are calculated using the number of subjects in the ITT Population for each treatment as the denominator.

P-values determined using the normal approximation to the binomial distribution using observed responses.

ITT= Intent-to-Treat

NA = Not Applicable

Source: Listing 16.2.6.3.1

Programming Notes: Continue for all cycles through Cycle 11.

Use same structure for Table 14.2.2.1.2 (PP Population) with PP instead of ITT in the two appropriate footnotes and the last footnote changed to "Source: Listings 16.2.6.3.1, 16.2.1.2".

Table 14.2.2.2.1

Best Overall Response
ITT Population

	CF102	Placebo
Best Overall Response, n (%)	(N=xx)	(N=xx)
CR	xx (xx.x)	xx (xx.x)
PR	xx (xx.x)	xx (xx.x)
SD	xx (xx.x)	xx (xx.x)
PD	xx (xx.x)	xx (xx.x)
Total	xx	xx
ORR	xx (xx.x)	xx (xx.x)
P-value	0.xxxx	
DCR	xx (xx.x)	xx (xx.x)
P-value	0.xxxx	

CR=Complete Response, PR =Partial Response, SD =Stable Disease, PD=Progressive Disease

ORR=Objective Response Rate= proportion of subjects who have response of CR or PR

DCR=Disease Control Rate= proportion of subjects who have response of CR. PR, or SD

Percentages are calculated using the number of subjects in the ITT Population for each treatment as the denominator.

P-values determined using the normal approximation to the binomial distribution using observed responses.

Best Overall Response is determined for the entire duration of the study and is counted once per subject, although it may occur more than once.

ITT= Intent-to-Treat

NA = Not Applicable Source: Listing 16.2.6.3.1

Programming Notes: Best Overall Response is determined for the entire duration of the study. Use same structure for Table 14.2.2.2.2 (PP Population) with PP instead of ITT in the two appropriate footnotes and the last footnote changed to "Source: Listings 16.2.6.3.1, 16.2.1.2".

Table 14.2.3.1 WBC A3AR expression ITT Population

		CF102	Placebo
Visit	Statistic	(N=xx)	(N=xx)
Baseline	n	XX	XX
	Mean (SD)	xxx.x (xxx.xx)	xxx.x (xxx.xx)
	Median	XXX.X	XXX.X
	Min, Max	XXX, XXX	XXX, XXX
Cycle 3 Day 1	n	XX	XX
	Mean (SD)	xxx.x (xxx.xx)	xxx.x (xxx.xx)
	Median	XXX.X	XXX.X
	Min, Max	XXX, XXX	XXX, XXX
CFB at Cycle 3 Day 1	n	XX	XX
	Mean (SD)	xxx.x (xxx.xx)	xxx.x (xxx.xx)
	Median	XXX.X	XXX.X
	Min, Max	XXX, XXX	XXX, XXX
Cycle 5 Day 1	n	XX	XX
	Mean (SD)	xxx.x (xxx.xx)	xxx.x (xxx.xx)
	Median	XXX.X	XXX.X
	Min, Max	XXX, XXX	XXX, XXX
CFB at Cycle 5 Day 1	n	XX	XX
	Mean (SD)	xxx.x (xxx.xx)	xxx.x (xxx.xx)
	Median	XXX.X	XXX.X
	Min, Max	XXX, XXX	XXX, XXX

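### ORR and DCR percentages use the full ITT (or PP) denominator, but the shells base the p-values on observed responses and SAP 7.6.4 leaves the test's n undefined, so a p-value need not test the rates printed with it

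*SAP*

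**What the plan says.** Two footnotes stand close together under shell Table 14.2.2.1.1 (Overall Response by cycle) and again under Table 14.2.2.2.1 (Best Overall Response). For the rates: "Percentages are calculated using the number of subjects in the ITT Population for each treatment as the denominator". For the tests: "P-values determined using the normal approximation to the binomial distribution using observed responses". The PP versions keep the structure and replace ITT with PP.

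SAP 7.6.4 specifies the test: "The between-treatment comparison will be performed using the normal approximation to the binomial distribution (NAB) with unequal variances, as follows". The sample sizes in the formula, n_CF and n_0, are described for each cycle only as numbers of "subjects for CF102 and Placebo, respectively, and let". Nothing there ties them to the ITT N or to the number assessed.

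Four other provisions decide who has a recorded response:

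- **SAP 6.1, imaging after PD:** "Further imaging or target lesion measurements will not be required and all other trial visits and procedures will continue". Protocol 9.2.12 says the same.
- **SAP 6.1, carrying PD forward:** a later PD "will be included at every cycle for which the Overall Response is recorded through Cycle 11", so it is carried only where something was recorded.
- **SAP 8:** tumor response is not among the variables imputed by LOCF, and nothing is imputed for discontinuation.
- **SAP 9:** no subject was excluded from the ITT Population.

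The Table Format Specification in the shells replaces the p-value by NA in two cases. One is a Total below 2 in either arm. The other is a category equal to Total, "i.e. a percent of 100 for that category, for both treatment groups".

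**The concern.** A subject who died before a scan, missed it, or was not re-imaged after PD has no recorded response at that cycle. Such a subject counts in the printed percentage. If the test uses only observed responses, the same subject is absent from the test.

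The p-value then compares response among those alive and scanned, a set that treatment can itself change. It can disagree with the percentages beside it in significance and even in direction. ORR and DCR are named secondary endpoints, and readers will take each p-value as a test of the rates it accompanies.

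**Working it through.** **Which n do the documents imply?** Among the shells for categorical variables, only the response tables print p-values, and they carry the matching NA footnote, so the NA rule appears to be meant for them. If Total were the ITT N (about 52 and 26), a Total below 2 could not occur. Equating a category equal to Total with 100 percent also conflicts with percentages based on ITT N, unless everyone was assessed. Both features fit Total being the assessed count. This supports the observed-case reading but does not prove it.

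**Inputs**

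- About 78 subjects at 2:1 (SAP 3.1), taken as 52 v 26.
- Hazard ratio 0.5 (Protocol 12.2).
- Control median OS after sorafenib failure generally no more than 2 months (Protocol 4.5.2), taken as 60 days. For the range, 3.5 and 5.5 months (105 and 165 days), the figures the same section gives for Child-Pugh B overall.
- Scans every 8 weeks, so days 56 and 112 (SAP 2.2).
- Assumptions: exponential survival, every survivor scanned, and all response counts.

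**The plan's own figure.** The response tables state no figure. The one numeric design figure is 75 deaths for 80% power. Schoenfeld's formula gives (1.960+0.842)² / [(2/3)(1/3)(ln 0.5)²] = 73.5, or 74 deaths, and 75 deaths give 80.8% power. The figure reproduces, but the point does not depend on it.

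**Numbers scanned at day 56.** Placebo survival is 0.5^(56/60) = 0.524, and 26 × 0.524 ≈ 14. CF102 survival is 0.524^0.5 = 0.724, and 52 × 0.724 ≈ 38. The same calculation at day 112 gives about 27 v 7.

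**Test (SAP 7.6.4).** Z = (p_CF − p_0) / √[p_CF(1−p_CF)/n_CF + p_0(1−p_0)/n_0], two-sided.

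Worked case, 19 v 7 with disease control at day 56:

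- ITT n: 0.365 − 0.269 = 0.096; variance 0.00446 + 0.00757 = 0.01203; Z = 0.88, p = 0.38.
- Observed n: 19/38 v 7/14, 0.500 v 0.500; Z = 0, p = 1.00.

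| Assumed counts (CF102 v placebo) | Printed rates | p from printed rates | Observed rates | Observed-case p |
|---|---|---|---|---|
| Day 56, 19 v 7 | 36.5% v 26.9% | 0.38 | 50.0% v 50.0% | 1.00 |
| Day 56, 26 v 7 | 50.0% v 26.9% | 0.038 | 68.4% v 50.0% | 0.23 |
| Day 56, 15 v 10 | 28.8% v 38.5% | 0.40 | 39.5% v 71.4% | 0.027 |
| Day 112, 14 v 4 | 26.9% v 15.4% | 0.22 | 51.9% v 57.1% | 0.80, opposite sign |

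With 38 v 14 scanned there are 37 × 13 = 481 pairs of counts that avoid 0 and 100 percent. The two bases fall on different sides of 0.05 in 108 of them and differ in sign in 58. These are counts of possibilities, not probabilities.

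**Range at day 56, control in about half of those scanned**

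| Control median, HR | Scanned | p from printed rates | Observed-case p |
|---|---|---|---|
| 60 days, 0.5 | 38 v 14 | 0.38 | 1.00 |
| 105 days, 0.5 | 43 v 18 | 0.51 | 0.93 |
| 165 days, 0.5 | 46 v 21 | 0.62 | 0.86 |
| 60 days, 1.0 | 27 v 14 | 1.00 | 0.91 |

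The two bases agree exactly when every ITT subject has a recorded response.

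**The case against.** The best defence is that the footnote need not mean observed cases. It could mean that LOCF is not used, since the neighbouring by-visit shells carry an LOCF footnote and the response shells do not. It could also refer to the unpooled variance built from observed proportions, which SAP 7.6 and 7.6.4 stress. SAP 7.1 assigns all efficacy analyses to the ITT Population. The NA rule is a general formatting convention and may be untailored. In some of the cases it covers, such as every response being PD in both arms, Z is undefined with either n. This stands as far as it goes: the observed-case reading is the natural one, not a certainty. But naming a population does not define n. Under the other readings what remains is an undefined n beside an unexplained footnote, and the same definition cures it.

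Three further points stand:

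- The shell prints N, each category count and Total, so a careful reader could recompute either version.
- The mismatch need not change a conclusion. In 373 of the 481 pairs both bases fall on the same side of 0.05.
- The 15 v 10 row pairs a halved death rate with much worse disease control on CF102. It shows what can happen, not what is likely.

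A reader might infer that from Cycle 5 the tested set consists largely of subjects who have not progressed. The documents do not support that. Scans after PD are not required, but they are not barred. End-of-study, follow-up and unscheduled scans are assigned to the next cycle, and any response recorded after PD is kept as PD. No rate of scanning after PD is given.

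**Conclusion.** The point holds as an unreconciled pair of footnotes together with an undefined n. Followed as most naturally read, they give secondary-endpoint p-values that do not test the printed rates and that condition on being alive and scanned.

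The reach differs by table. In the by-cycle tables, death before the scan, a missed scan and no re-imaging after PD all remove a subject from the test. In Best Overall Response a progressed subject keeps PD, so only subjects with no evaluable post-baseline response leave it.

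The size is illustrative: p=0.38 against 1.00 in the equal-control case at week 8, with crossings of 0.05 in both directions under other counts. It rests on the assumed survival, complete scanning of survivors and invented response counts. A reader might infer that the trial's response p-values are wrong or favour one arm. The documents contain no response data and support neither inference. The OS logrank analysis is unaffected.

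**What to change.** 1. In SAP 7.6.4, define n_CF and n_0 as the denominator used for the printed percentages: ITT N, or PP N in the PP tables, at every cycle and for Best Overall Response.
2. For ORR, state whether it is limited to subjects with measurable disease at entry, as the protocol defines OR, and use that denominator for both rate and test.
3. Count death, missing and NE as non-response for ORR and as no disease control for DCR. Carrying PD forward is then not needed for either test. Say also where the Non-CR/non-PD category of SAP Appendix B goes, since the shells have no row for it.
4. Delete the words about observed responses from the main-table footnotes, and keep the observed-case result as a labelled sensitivity analysis.
5. Record the change in SAP Section 9 as made after unblinding. SAP Version 7.0 already contains decisions made after unblinding.

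The cost is wording, a change of denominator in the program and one extra labelled analysis. Lower by-cycle rates will feed the test, and the change is post hoc, which is why the observed-case result should stay visible.
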